6.1 Visit Procedures

Visits are designated as shown below to facilitate scheduling of procedures and recording of study-related data. All study visits will be numbered as a single consecutive series. Variations outside specific windows will be recorded as a protocol deviations.

Visit 1	Screening and enrollment. (If screening and enrollment require more than one visit, they will be designated 1a, b, etc.)
Visit 2	Administration of Panhematin [™] or placebo. (This visit might be on the same day as Visit 1.) If additional days are needed at the study site, such as for additional doses of study drug for prevention, or for treatment of an attack of porphyria, these will be designated 2a, b, etc.
Visit 3,4,5,6, 7 & 8	These will occur in person or by phone at weekly intervals for the first month to determine efficacy, and 3 and 6 months after completion of blinded treatment to record long terms effects of the study treatment and subsequent course and clinical treatment of the disease

6.1.1 Visit 1 – Screening and Enrollment

Patients will be fully informed about the purposes and procedures of the study, orally and in writing, and asked to sign an informed consent form approved by the IRB, which describes study procedures and the risks and potential benefits of the study. Patients will be screened for eligibility and enrolled at Visit 1. Any additional studies needed to determine eligibility will be done at that time.

Procedures:

After enrollment each subject will be allocated a unique study enrollment number. If the inclusion and exclusion criteria (see below) are satisfied, the patient will be randomized during the screening visit or before and assigned a unique study randomization number. The following will be performed and recorded in the CRF:

- 1. Checks of Inclusion and Exclusion Criteria.
- 2. Demographic Information, to include:
 - Date of Birth
 - Sex
 - Race and ethnicity

- 3. History, to include:
 - Year of first porphyria attack
 - Number of attacks during the past 6 months
 - Attacks related to the menstrual cycle or not
 - Attacks related to other precipitating factors (harmful drugs, nutritional alterations, etc. or not
 - Time of onset of the most recent attack
 - Previous treatment with Panhematin™
- 4. Concomitant illnesses
- 5. History of allergy
- 6. Concomitant medications
- 7. Use of opioid agonists during the previous 6 months
- 8. Physical Examination, including:
 - a. Body height and weight
 - b. Vital Signs
- 9. Electrocardiogram, if clinically indicated
- 10. Recording of porphyria-related signs and symptoms
- 11.Blood samples will be drawn for testing, to include erythrocyte PBGD activity, serum or plasma PBG and porphyrins, complete blood counts, and metabolic and hepatic panels
- 12.Urine sample will be collected for assessment of urine ALA, PBG, and porphyrins.
- 13. Fecal sample will be collected for porphyrins.
- 14.Blood sample for DNA isolation and mutation analysis (unless done previously). This is now considered standard of care diagnostic testing for porphyrias, and is widely available. A separate consent form for this testing will be provided only if required by the testing laboratory.
- 15. Urine pregnancy tests (for females of childbearing potential only).

6.1.2 Visit 2:

Procedures:

The following will be performed and recorded in the CRF (at time of treatment):

- 1. Concomitant medications, and any changes not recorded previously
- 2. Vital Signs
- 3. Recording of porphyria-related signs and symptoms
- 4. Urine, blood and fecal samples for ALA, PBG and porphyrins (pretreatment)
- 5. Recording of adverse events

6. Administration of a dose of study treatment (Panhematin[™] or placebo)

6.1.3 Visit 3, 4, etc.

Procedures:

Recording of clinical information and obtaining samples, as appropriate clinically.

Observation and treatment of any attacks or symptoms of porphyria.

6.2 Assessments for Efficacy

6.2.1 Clinical improvement

Attack prevention will be assessed especially over the 4 weeks following study drug administration. The expectation is that efficacy in preventing an attack is most likely within the first week, or within the time interval between usual prophylactic dosing.

6.2.1.1 Number of attacks and porphyria-related signs and symptoms

At the post-treatment visits the patients will be queried about symptoms attributable to porphyria, treatment that was given for such symptoms and any doctor for hospital visits or admissions since the previous visit. Symptoms recorded will include pain, nausea, vomiting, constipation and specified neurological and psychiatric symptoms. This information will be recorded on the CRFs.

6.2.1.2 Other clinical information

Use of Panhematin[™], glucose loading and potent opioid agonists since the last visit including the generic and trade names, dose, route of administration and time of each dose will be recorded.

6.2.2 Biochemical measures of improvement

Biochemical measures, to include urinary ALA, PBG and porphyrins, plasma PBG and porphyrins and fecal porphyrins will be measured at each visit, but will be optional for the follow up visits at 1, 2, 3, and 4 weeks and 3 and 6 months. Analyses will be performed at the Porphyria Laboratory of the University of Texas Medical Branch.

6.3 Safety Assessment

6.3.1 Symptoms

Any new symptoms not related to porphyria will be recorded during the treatment period.

6.3.2 Physical Examination

Physical examination, to include vital signs, weight, body mass index (BMI) and evaluation of the major systems will be recorded at each visit, but will be optional for the follow up visits. Height will be recorded only at Visit 1.

Porphyria Laboratory and Center Date: June 18, 2019 IND 13,929

6.3.3 Blood counts and chemistries

Blood samples will be drawn for complete blood counts and metabolic, hepatic and coagulation panels at each visit, but will be optional for follow up visits. Analyses will be performed either by the hospital laboratory. The site investigator will review the report, sign and date it, and comment on any laboratory abnormality that is judged to be clinically relevant. A clinically relevant abnormality is defined as one that suggests a disease or organ toxicity and is of a severity that requires active management (e.g. change in treatment, more frequent follow-up or diagnostic investigation).

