5.6 Treatment of acute attacks during the study

Attacks during the study that occur at the study site will be treated at the study site with the usual hemin regimen of 4 mg/kg body weight daily for 4 days, or longer if clinically indicated, as part of the study. Attacks that occur after the patient leaves the study site and returns home will be treated in the manner considered optimal by the patient's physicians. Such treatment will be recorded but not prescribed by the protocol. Study site physicians will be available to provide advice on management, as appropriate. This will not be considered formally as rescue treatment since it is not prescribed in the study protocol. It will be recommended that Panhematin[™] be reconstitution with human albumin, as described above, since this is now considered optimal ⁹. Blinding of the study treatment will be maintained during unblinded treatment of any acute attacks, unless doing so would compromise patient safety.

Administration of two Panhematin[™] doses of 4/mg/kg doses daily was common in the past, although a single daily dose for 4 days is now more commonly recommended ⁹. When two doses are given, an interval of at least 6-8 hours is customary. During this study, a need to give two doses of Panhematin[™] within a period of 12 hours will occur only if an acute attack develops and needs to be treated within 12 hours of the previous study dose of Panhematin[™] or placebo.

As noted above, if open label treatment with Panhematin[™] is required less than 12 hours after a blinded infusion, the first infusion for treating the acute attack will also be blinded, and the first infusion will be Panhematin[™] if the patient was randomized to placebo, and will be placebo if the patient was randomized to Panhematin[™]. This will avoid unblinding of the randomly assigned study treatment.

Symptomatic treatment for pain, nausea and vomiting will be given as needed to control these symptoms of the porphyric attack, which can be severe. These are regarded as expected treatments rather than rescue treatments and are not a prescribed part of this study.

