12.2.2 Safety variables

As noted earlier, safety endpoints will include:

- Symptoms
- Findings on physical examination including vital signs
- Routine clinical testing daily including
 - Complete blood counts
 - Metabolic and liver panels
 - Coagulation panel (platelets, prothrombin time and partial thromboplastin time)
- Unexpected adverse events

These will be subjected to descriptive analyses and differences between the treatment groups analyzed for significance as described below.

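### How much post-dose safety testing a patient receives depends partly on having an attack on site, yet Section 12.2.2 compares the arms on every result, which tilts the comparison toward hemin looking as safe as placebo

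*Combined protocol and SAP*

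**What the plan says.** - **Panels (Section 6.3.3).** Blood counts and metabolic, hepatic and "coagulation panels at each visit, but will be optional for follow up visits". No draw time relative to the infusion is given.
- **Examination (Section 6.3.2).** Physical examination "will be recorded at each visit, but will be optional for the follow up visits". Follow-up visits may be by telephone.
- **Visit labels (Section 6.1).** Extra days on site carry the Visit 2 label whether they are needed "such as for additional doses of study drug for prevention" "or for treatment of an attack of porphyria, these will be designated 2a, b, etc". They are not follow-up visits.
- **Visit 2 procedures (Section 6.1.2).** The list names no safety panel, and the samples it does name are for porphyrin precursors and porphyrins, taken before treatment.
- **Visits 3, 4, etc. (Section 6.1.3).** Two items are listed: "Recording of clinical information and obtaining samples, as appropriate clinically" and "Observation and treatment of any attacks or symptoms of porphyria".
- **Attack treatment (Section 5.6).** On site, the "usual hemin regimen of 4 mg/kg body weight daily for 4 days", or longer if clinically indicated. Attacks after the patient goes home are managed by the patient's own physicians and only recorded.
- **Analysis (Section 12.2.2).** Routine testing is described as daily. Safety variables are summarised and "differences between the treatment groups analyzed for significance as described below". Nothing limits the comparison to assessments due in every patient. Section 11 puts all exposed patients in the safety analysis and states no cut-off at open-label hemin.

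**The concern.** Sections 6.1, 6.3.2 and 6.3.3 together make a panel and an examination compulsory on each day a patient is on site for an attack. A single-infusion patient with no attack goes home to optional checks. The number of times an abnormality can be found after dosing is therefore partly a consequence of the primary efficacy outcome.

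Coagulation abnormality is one of the primary safety parameters (Section 2.1), and showing that hemin is as safe and well tolerated as placebo is a primary objective (Section 2). Section 13.1 describes the hemin anticoagulant effect as transient, so a panel not drawn at the time cannot be made up later.

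If hemin prevents attacks, two things push the same way:

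- **Detection.** Placebo patients are looked at more often, so more incidental abnormalities are found in that arm.
- **Attribution.** Those extra looks usually happen while the placebo patient is receiving open-label hemin, so real hemin effects can be counted under placebo.

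**Working it through.** **Inputs**

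- Recurrence probabilities 0.8 (control) and 0.2 (treatment), with 0.38 as the alternative treatment value: Section 12.4, given there as illustrations.
- 4 days of on-site treatment per attack: Section 5.6.
- Six follow-up visits with optional testing (Visits 3 to 8): Section 6.1.
- Assumptions, not in the documents: one attack per affected patient; one panel per attack-treatment day; a share *f* of attacks treated on site, equal in both arms; uptake *q* of optional panels; *S* compulsory post-dose panels shared by both arms.

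**Step 1: the plan's own figures.** Pooled normal approximation, two-sided 5%, no continuity correction:

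power = Φ{ [|p1 − p2| − 1.96·√(2p̄(1 − p̄)/n)] / √([p1(1 − p1) + p2(1 − p2)]/n) }

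- 0.8 vs 0.2, n = 10 per group: (0.6 − 1.96 × 0.2236)/0.1789 = 0.904, so power is 81.7%. The plan states 80%.
- 0.8 vs 0.38, n = 20 per group: power is 79.4%; 80% needs 21 per group. The plan states 20.

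The rates are being read as the plan uses them.

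**Step 2: compulsory attack-day panels per patient** = 4 × f × p. With f = 1:

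- 0.8 vs 0.2: 3.2 and 0.8, ratio 4.0, gap 2.4.
- 0.8 vs 0.38: 3.2 and 1.52, ratio 2.1, gap 1.68.

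The share *f* cancels from the ratio but sets the gap. At 0.8 vs 0.2 the gap is 4 × f × 0.6: 2.4 at 100% on site, 1.2 at 50%, 0.6 at 25% and 0.24 at 10%.

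**Step 3: count the other panels.** Panels per patient = S + 6q + 4fp.

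One shared post-dose panel (S = 1), no optional panels (q = 0):

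| Share on site | Ratio, 0.8 vs 0.2 | Ratio, 0.8 vs 0.38 |
|---|---|---|
| 100% | 4.2/1.8 = 2.33 | 4.2/2.52 = 1.67 |
| 50% | 2.6/1.4 = 1.86 | 2.6/1.76 = 1.48 |
| 25% | 1.8/1.2 = 1.50 | 1.8/1.38 = 1.30 |
| 10% | 1.32/1.08 = 1.22 | 1.32/1.15 = 1.15 |

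Other cases at 0.8 vs 0.2 with all attacks on site:

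- Four shared panels, as in a multi-dose regimen: 7.2/4.8 = 1.5.
- No shared panel, optional panels taken at 25%, 50% or 100% of follow-up visits: 4.7/2.3 = 2.0, 6.2/3.8 = 1.6, 9.2/6.8 = 1.4.

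S = 1 applies to a single-infusion patient only if the Visit 2 panel is drawn after the infusion. Section 6.3.3 requires a Visit 2 panel but does not say when. If it is drawn before dosing, that patient has no guaranteed post-dose panel without an on-site attack, and the Step 2 ratio applies to compulsory panels.

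**The case against.** A reader might infer that placebo patients will be tested four times as often and that hemin will therefore look safer. The documents do not support that.

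- **The 4:1 ratio is a ceiling.** It is 0.8/0.2 from a power illustration, counting only compulsory attack-day panels. The plan's second illustration gives 2.1.
- **Many attacks may bring no study panel.** Most patients receive a single weekly dose, Visit 2 may last one day, and Section 3.2 expects long-distance travel. Home attacks trigger no required test.
- **Equal on-site shares are doubtful.** Section 1.1 says hemin takes 24–48 hours to lower ALA and PBG, so attacks during a short site stay may be those least likely to differ by arm.
- **Compulsory testing on attack days is an inference.** Section 6.1.3 also places attack treatment under Visits 3, 4, etc., with clinically driven sampling.
- **Some compulsory days are not attack-driven.** Extra study-dose days occur in both arms.
- **Adverse events are recorded at every visit (Section 6.3.6),** and nausea and vomiting are not panel results.

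A reader might also put a figure on the artefact. At an assumed 5% abnormality rate per panel, four independent panels give 1 − 0.95⁴ = 0.185, hence 14.8% of placebo and 3.7% of hemin patients. That needs a rate found nowhere in the documents, independent daily panels in one patient, and every attack on site. At 10% on site it is about 1.5% vs 0.4%. With 10 per arm, even the 11-point gap is about one patient. I do not rely on it.

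These points limit the size but leave the mechanism. Clinically driven sampling still depends on outcome, because an ill patient is sampled and a well one on the telephone may not be. Recording adverse events at every visit does not equalise laboratory findings, since an abnormality exists only if a panel is drawn. Nor can the effect be treated as fully separate from open-label hemin: the on-site days counted here are normally the hemin-treatment days, so extra looking and misattribution occur together.

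**Conclusion.** The concern holds in a limited form. Read literally, the plan makes post-dose safety testing partly dependent on having an attack, its sections disagree on when testing is due, and the between-arm comparison has no restriction to offset this. If placebo patients have more attacks, the bias is toward hemin looking as safe as placebo.

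At the plan's illustrative rates, the imbalance in compulsory attack-day panels is at most about 4:1 (0.8 vs 0.2) or about 2:1 (0.8 vs 0.38). With one shared post-dose panel it is about 1.2 to 2.3 across both rate pairs and on-site shares of 10% to 100%; optional or multi-dose-day panels bring it down as well. At 0.8 vs 0.2 the absolute gap runs from 2.4 panels per patient to 0.24 over that range. These results assume one 4-day attack per affected patient and equal on-site shares. The documents do not show that a distorted safety result will follow; they leave nothing in the analysis to prevent one.

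**What to change.** 1. Reconcile Sections 6.1, 6.1.3, 6.3.2, 6.3.3 and 12.2.2 so that one rule states when panels and examinations are due.
2. Give the panel and examination already required at Visit 2 the same stated time after the blinded infusion in both arms.
3. In Section 12.2.2, limit between-arm tests of laboratory, coagulation and examination findings to such commonly scheduled assessments.
4. List findings from attack-treatment days and extra symptom visits by arm without a test, marking those that follow open-label hemin.
5. Report the number of post-dose assessments per patient by arm.

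Item 2 is needed for item 3 to work: without a common post-infusion time, the restricted test has no guaranteed post-dose data for single-infusion patients. Timing the draw alone is not enough either, because Section 12.2.2 would still pool the attack-day results with it.

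The cost is protocol and analysis wording, one extra table, and one draw and examination held to a set time. Fewer samples enter the test, but those that do are comparable between arms. No treatment rule changes.

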6.3.4 Urinalysis

A standard urinalysis will be performed at UTMB, using a urine strip, at Visit 1.

6.3.5 Pregnancy test

For women of childbearing potential a pregnancy test (urine hCG) will be performed at UTMB at Visit 1. Since pregnancy is not a reason for avoiding treatment with Panhematin[™], a positive pregnancy test will not exclude a patient from entering or continuing the study. Pregnancy will be recorded as a concomitant condition.

6.3.6 Adverse Events

Adverse Events will be recorded at each visit.

7. Adverse Events

7.1 Definitions (ICH)

Adverse Event (AE):

An AE is any untoward medical occurrence in a patient or clinical investigation subject administered a pharmaceutical product and which does not necessarily have a causal relationship with this treatment. The following should not be recorded as AEs, if recorded at screening:

- Pre-planned procedure, unless the condition for which the procedure was planned has worsened from the first trial related activity after the subject has signed the informed consent.
- Pre-existing conditions found as a result of a screening procedure.

Clinical Laboratory Adverse Event:

A clinical laboratory AE is any clinical laboratory abnormality that suggests a disease and/or organ toxicity and that is of a severity that requires active management (i.e. change of dose, discontinuation of drug, more frequent follow-up or diagnostic investigation). Clinical laboratory abnormalities that are found at screening and that fall under the above description should be recorded as a concomitant illness.

Serious Adverse Event (SAE):

A SAE is defined and distinguished from a non-serious AE as follows:

Serious/Non-Serious Adverse Event Definitions:			
Serious Adverse	An SAE is any untoward medical occurrence that at any		
Event	dose:		
(SAE)	 results in death, is life-threatening*, requires inpatient hospitalization or prolongation of existing hospitalization, results in persistent or significant disability/incapacity, 		
	 is a congenital anomaly/birth defect is an important medical event that may not result in death, be life-threatening*, or require hospitalization when, based upon appropriate medical judgment, it may jeopardize the patient or subject and may require medical or surgical intervention to prevent one of the outcomes listed in this definition. 		
Non-Serious	A non-serious adverse event is any AE which does not		
Adverse Event	fulfill the definition of an SAE		
* The term life-threatening in the definition of serious adverse event refers to an			

event in which the subject was at risk of death at the time of the event. It does not refer to an event which hypothetically might have caused death if it was more severe.

8. Case Report Forms

Case Report Forms (CRFs) will be prepared at UTMB for this study.

8.1 Rules for Completing CRFs

CRFs may be completed by investigators, coordinators and study nurses. They will print legibly using a black ballpoint pen, and ensure that all relevant questions are answered and that no data entry spaces are left empty.

Any assessment or test data that was not done and will not be available is indicated by writing "N/D" (Not Done) in the answer field. If the question is irrelevant or not applicable, this is indicated by writing "N/A" (Not Applicable) in the field.

The investigator and site study team must ensure that all information derived from source documentation is consistent with the source information. By signing the Affirmation Statement, the Investigator confirms that the information in the CRF is complete and correct.

Porphyria Laboratory and Center Date: June 18, 2019 IND 13,929

8.2 Corrections to CRFs

Corrections to the data on the CRFs must only be made by drawing a straight line through the incorrect data and then writing the correct value next to data that has been crossed out. Each correction must have initials of the individual who made the correction and the date of the correction. An explanation for the correction should also be written next to the correction, if necessary for clarity. If corrections are made after the date of the Investigator's signature on the Affirmation Statement, the Statement must be signed and dated again by the Investigator.

8.3 CRF Review and Data Entry

The original CRFs are reviewed by the investigator and study coordinator during the study and after completion of each subject. CRFs are finalized after no further corrections or amendments to the content are expected. After CRFs are verified and finalized, data will be compiled for analysis by the study biostatistician. CRFs will be archived at a secure archiving location at UTMB.

9. Monitoring Procedures

Safety Monitoring Plan

The risk level for this study is judged to be low, since treatment with Panhematin[™] is already part of clinical practice and treatment of enrolled patients, and no investigational products are involved. Although use of albumin for reconstituting Panhematin[™] is an off-label method, there is strong evidence and considerable experience to suggest that this increases safety. Potential risks of the study are described in detail under Assessment of Risks (See Section **13.1** below). Because this is not a Phase III clinical trial, a Data and Safety Monitoring Board (DSMB) is not required.

Recruitment, enrollment, retention, adverse events, and study procedures will be monitored carefully by the PI and study coordinator(s). They will review individual subjects' study records to ensure that appropriate safety procedures are being followed, that protocol requirements are being adhered to, and that data is accurate, complete, and secure. Study records include consent forms, case report forms, flow charts, data forms, laboratory specimen records, inclusion and exclusion criteria forms, adverse event logs, and medical charts. Investigators will review available data at study meetings that usually occur monthly, and discuss any instances of adverse events or unexpected problems encountered regarding patient safety or data collection.

Plan for Adverse Event (AE) Reporting. See Section **7**. The investigators will be notified immediately if an AE occurs, and a medical member of the team will evaluate the patient and enter a note in the CRFs. The investigators will be responsible for notifications to the IRB and others, as appropriate. In particular, all unanticipated, serious, fatal and/or life-threatening adverse events will be reported to the IRB, and others as required, within 24 h of occurrence or notification. The investigators, and the IRB are primarily responsible for determining whether modifications to the protocol and consent form are required. If a determination is

made that participants are found to be exposed to excessive risks in relation to anticipated benefits, the study may be immediately suspended, unless corrective changes can be made quickly. Studies will continue after modifications are made that are deemed to result in an acceptable risk/benefit ratio. Aggregate reports of SAEs will be prepared on an annual basis and forwarded to the IRB and others as required.

Plan for Safety Review. Every effort will be undertaken to monitor and minimize the risks to subjects. Prior to obtaining informed consent, subjects will be encouraged to thoroughly read the informed consent form and ask questions regarding the outlined procedures and risks, and be informed of all tests involved in the screening process.

Data Monitoring Plan

To ensure data quality and study integrity, all study data will be collected by the research team, recorded on data flow sheets or case report forms, and stored in locked file cabinets or secure electronic databases. The PI will be responsible for ongoing monitoring of data integrity and patient safety.

This is an investigator-initiated single site clinical study that is supported by a grant from the FDA Office of Orphan Product Development. Some additional grant support as well as study drug are provided by Recordati Rare Diseases. External monitoring will not be required. Data monitoring will be done, as described above, by the investigators and study coordinator. The following items must be verifiable in source documentation:

- Existence of subject (initials, date of birth)
- Confirmation of participation in trial (subject ID, trial ID and signed and dated research consent form)
- Diagnosis/indication under investigation
- Visit dates
- Adverse events or signs and symptoms (description and duration)
- Relevant medical history and/or concomitant illness(es)
- Concomitant medications
- Blood pressure, pulse, weight and height
- Reason for exclusion or withdrawal

The data recorded in the CRF are considered as source data.

10. Data Management

The PI and research staff will be responsible for management of data as recorded on the CRFs or secure electronic databases. Data downloaded from the database for analysis will identify subjects by study number, without personal identifiers. The identity of subjects will be excluded from all presentations and publications.

Porphyria Laboratory and Center Date: June 18, 2019 IND 13,929

11. Evaluability of Subjects for Analysis

The data analysis for efficacy will include all randomized subjects who were randomized and exposed to the study drug or placebo, fulfilled inclusion and exclusion criteria, and for whom there were no protocol violations or deviations that affect assessments of efficacy. All subjects exposed to active drug or placebo will be included in the safety analysis.

The decision to exclude any subject or observation will be recorded, and the reasons for their exclusion will be documented and signed by those responsible for the exclusion. This documentation will be stored with other trial documentation.

12. Statistical Analyses

Statistical analyses will be conducted in the Office of Biostatistics at UTMB by [name], Assistant Professor in the Division of Epidemiology and Biostatistics of the Department of Preventive Medicine and Community Health at UTMB.

